**Figure 14B**

*Figure 14B: Determining acceptable single antigen bead strength by using the sum of the highest DSA values for class I and class II beads versus BPFXM. ♦ Patients with no ABMR episodes, ■ patients with an ABMR episode within 42 day. ♦ A patient with ABMR within 50 to 200 days and patients with ▲ ABMR episodes after 200 days.*

By using the criteria outlined, 74% (80/108) HS (C PRA>80%) DD recipients treated with desensitization (1/06-12/09) were transplanted. A total of 26% (28/108) patients remained on the waitlist during this period with mCPRA 95. Four of these patients were transplanted in 2010. Of the 80 patients transplanted, 42 (53%) were transplanted with a positive donor specific T and/or B cell flow cytometry XM. A total of 19 (24%) patients experienced ABMR +/- CMR ranging from 3 to 535 days post-transplant with a median of 109 days. Seven of these patients were diagnosed with ABMR +/- CMR within the first 42 days. Two patients were diagnosed with late ABMR +/- CMR at post-transplant days 144 and 249. One of these patients had CMV detected by PCR before the diagnosis of ABMR and one patient had CMV detected by PCR at the time of ABMR diagnosis.. Another patient had Parvovirus B19 positive PCR reaction prior to the diagnosis of ABMR (post-transplant day 535). One patient was noncompliant (post-transplant day 139) and lost the graft. Twenty-eight patients (mCPRA 91) were transplanted with a negative donor specific flow cytometry XM. Pretreatment samples were available for 25 of these 28 patients and showed all pretreatment XMs were negative with the donor samples. Among these 28 patients, none had ABMR and 8 had CMR. The CMR occurred between 15 and 773 days post-transplant with the median time at 58 days. A total of 10 patients received zero HLA ABDR mismatched grafts (mCPRA 90), one had ABMR after 101 days post-transplant and one had CMR at 404 days post-transplant.

[figure not shown]
In this data set of 108 patients, we saw an ABMR rate of 24% using careful selection criteria based on FCMX and DSA data at transplant. When compared a concomitant group of non-sensitized patients transplanted during the same time period (N=190), we saw an ABMR rate of <1% in this non-sensitized, low risk group. Thus ABMR is very rare in non-sensitized patients and in patients who are DSA + but FCMX negative who have received desensitization prior to transplantation.

## 4.5 Monitoring for AE/SAEs Post-Transplant in HS Patients

Adverse events (AEs) and serious adverse events will be monitored post-transplant. These include careful attention to infectious complications potentially associated with IdeS® therapy.

Infectious complications associated with IVIG + rituximab desensitization and alemtuzumab induction therapy followed by maintenance therapy with tacrolimus, MMF and prednisone have been assessed by our group. Briefly, we evaluated 170 patients who were desensitized with IVIG + rituximab followed by alemtuzumab induction and maintenance therapy with tacrolimus, MMF and steroids. This was compared to a concomitant group of non-sensitized, low-risk transplants (N=191) who did not receive IVIG, rituximab or alemtuzumab (induction with IL-2R blockers). A careful analysis of all infections and serious infections that occurred over the next 4 years was compiled and is shown in Figure 15A &15B. Briefly, these data show that the use of this desensitization

[figure not shown]
**Figure 15A**

protocol followed with alemtuzumab induction does not increase the risk for common or serious infections post-transplant compared to a low risk group of patients. Serious infections were defined as any viral infection and fungal or bacterial infections requiring i.v. antibiotics or hospitalizations. Thus risk for infections in the study group (IdeS®) after desensitization will likely be similar and comparable to non-sensitized patients. All patients entered into this study will receive vaccinations for *Streptococcus pneumoniae* and *Neisseria meningitidis* pre-transplant.

In addition, all patients treated with IdeS® will also receive antibiotic prophylaxis with ciprofloxacin for 4 weeks post-transplant. It is also noted that our protocol includes a post-transplant dose of IVIG 2 gm/kg (maximum 140 grams) administered at 7 days post-transplant. This will provide additional anti-infective support during the IgG reconstitution after IdeS® therapy.

**Figure 15B**

15A & B: This figure shows the proportion of kidney transplant recipients who developed infections (all infections 15A, or serious infections 15B) post-transplant. Patients were in the low-risk group (non-Ritux #191) who did not receive IVIG/ritux or alemtuzumab or (Ritux #171) who received desensitization with rituximab, IVIG followed by transplantation. Follow up for up to 45 months shows that infection rates are similar. The commonest infection was urinary tract infection in both groups. The incidence of CMV was greater in the non-Ritux group while there were more BK infections in the Ritux group. No patients in the Ritux group developed PTLD or PML while 2 patients in the non-Ritux group developed PTLD.

#### 4.6 Infection Prophylaxis Protocols and Viral Monitoring Post-Transplant

All study patients, regardless of their cytomegalovirus (CMV) status, receive IV ganciclovir while inpatients and valganciclovir as outpatients for 6 months, with dose adjustments for renal function. Fungal prophylaxis was accomplished with fluconazole 100 mg daily for 1 month. *Pneumocystis jirovecii* pneumonia and bacterial prophylaxis is accomplished with trimethoprim 80 mg and sulfamethoxazole 400 mg daily for 12 months.

Viral polymerase chain reaction assays for CMV, Epstein Barr virus, Parvovirus B-19, Polyoma virus BK and JC will be performed on study patients monthly for 6 months post-

transplantation. Methodologies used for monitoring viral replication have been described previously.

#### 4.7 Outcomes of HS Patients vs. Non-Sensitized Patient Cohort

As part of the suggested revisions of this protocol, we have evaluated a group (N=170) of patients who underwent desensitization with IVIG + rituximab and were transplanted (2006-2010). This was compared to a group of non-sensitized patients who were transplanted during the same time period who did not receive IVIG, rituximab or alemtuzumab induction. The patient characteristics are shown in Table 1 below. Briefly, the only significant findings were the higher PRA in the Ritux group, more White (non-Hispanics) in the non-Ritux group, more females in the Ritux group, more lymphocyte depleting agents in the Ritux group and significantly longer dialysis times for the Ritux group. In Table 3, we see the outcomes up to 45 months post-transplant in the two groups. Briefly, there are no significant differences between the two groups in regards to patient and graft survival and infection rates however, there were more rejections in the Ritux group. As previously mentioned, the ABMR rate for sensitized patients (CPRA >80%) was 24% vs. <1% for the non-Ritux group.

**Table 3**

	RIT Group (N=170)	Non-RIT Group (N=191)	P
Age (years), mean $\pm$ SD	46.6 $\pm$ 13.6	51.9 $\pm$ 14.3	<0.001
Male gender, n (%)	69 (41.0)	141 (73.8)	<0.001
Cause of ESRD, n (%)			<0.001
DM	31 (18.2)	71 (37.2)	
HTN	21 (12.4)	28 (14.7)	
Glomerulonephritis	64 (37.7)	36 (18.9)	
Cystic Disease	6 (3.5)	18 (9.4)	
Other	28 (16.5)	36 (18.9)	
Unknown	20 (11.8)	2 (1.1)	
PRA, n (%)			<0.001
<10%	26 (15.3)	174 (91.1)	
10-80%	51 (30.0)	17 (8.9)	
>80%	93 (54.7)	0 (0)	
Type of donor, n (%)			0.027
Living	80 (47.1)	68 (35.6)	
Deceased	90 (52.9)	123 (64.4)	
Lymphocyte depletion, n (%)			<0.001
No	47 (27.6)	110 (57.6)	
Yes	123 (72.4)	81 (42.4)	
Race/Ethnicity, n (%)			0.015
White (non-Hispanic)	73 (42.9)	92 (48.1)	
Hispanic	44 (25.9)	64 (33.5)	
African American	29 (17.1)	22 (11.5)	
Asian	15 (8.8)	12 (6.3)	
Other	9 (5.3)	1 (<1)	
Length of follow-up (days), mean $\pm$ SD	479.0 $\pm$ 272.9	608.4 $\pm$ 301.6	<0.001
Dialysis Vintage (days), mean $\pm$ SD	1694.8 $\pm$ 1662.5	1059.0 $\pm$ 982.5	<0.001

Table 3 shows patient survival, graft survival, and number of patients who developed Infections in the Ritux vs. non-Ritux group.

**Table 4**

	RIT Group N=170	Non-RIT Group N=191	P
Overall Patient Survival, n (%)	165 (97.1)	183 (96.3)	NS
Overall Graft Survival, n (%)	154 (90.6)	170 (89.0)	NS
Rejection, n (%)	47 (27.7)	36 (18.9)	0.047
Any Infection, n (%)	88 (51.8)	103 (53.9)	NS
Bacterial Infections, n (%)	59 (34.7)	75 (39.1)	NS
Viral Infections, n (%)	37 (21.8)	48 (25.1)	NS
CMV viremia	17 (10.0)	29 (15.2)	NS
BKV viremia	18 (10.6)	11 (5.8)	0.092
Fungal Infections, n (%)	10 (5.9)	10 (5.2)	NS
Serious Infections, n (%)	39 (22.9)	49 (25.5)	NS

Table 4 shows the overall survival by treatment group and risk for common viral infections post-transplant. Briefly, no differences were seen between the two groups for any type of infection or serious infections.

## 5 Dosing of IdeS®

IdeS is a clear colorless liquid. It is formulated at 10 g/L in PBS and intended for intravenous administration after dilution. Refer to table 5 for composition.

**Table 5. Study drug**

Ingredient	Quantity (g/L)	Function
IdeS drug product	10	Active ingredient
Phosphate buffered saline:		
Potassium Chloride (KCl)	0.20	Buffer
Monopotassium Phosphate (KH 2 PO 4 )	0.20	Buffer
Sodium Chloride (NaCl)	8.0	Buffer
Disodium Phosphate (Na 2 HPO 4 )	1.43	Buffer

### 5.1 Storage and Handling

All patients will receive treatment with IdeS. IdeS will be supplied to the hospital pharmacy by Biovian in 7 mL vials packed into cartons containing 10 vials each. Vials should be kept dark at – 20°C. IdeS infusion solution will be prepared at the study unit. Administration will be performed using an infusion bag with a filter containing infusion set and an infusion pump. Details on preparation, labeling and administration of IdeS are described in the pharmacy manual. (see Appendix B).

#### 5.1.1 Collection, Transport & Shipping to the Laboratories

Samples for Anti-IdeS Antibody Levels will be collected according to the protocol outlined in Appendix C. These samples will be pooled and mailed to the

laboratories (Addresses listed in Appendix C). Thus, results will be available at the end of the study.

## 5.2 Patient Monitoring

Patients will be closely monitored for hypersensitivity reactions such as hives, urticaria, tightness of chest, wheezing, hypotension, and/or anaphylaxis during infusion of IdeS®, which are all common side effects of biological drugs. Patients will also be monitored for any signs of infections, although there were no signs of increased infection rates in healthy subjects who received IdeS. Patients with ongoing infections will not be included in the study.

## 5.3 Adverse Drug Reactions

A first in man single ascending dose study in 29 healthy subjects has previously been performed with doses up to 0.24 mg/kg BW with a favorable safety profile. Since IdeS degrades IgG there was concern that study subjects would have an increased risk of infection and that subclinical infections (e.g. pneumococci) would pose a problem. Therefore, subjects received antibiotic prophylaxis until plasma IgG levels had returned ( $>4.5$  g/L) and there were no signs of an increased rate of infections within the study group. The adverse events that were reported, none of which were reported as serious, were as anticipated from the biological nature of the drug. Hence, headache and fatigue were more common in the IdeS treated subjects compared to placebo. One possible infusion reaction was reported among the placebo treated subjects and one among the IdeS treated, the latter resolved within 15 minutes after treatment with antihistamine and glucocorticoids and the infusion was completed. All adverse events were mild or moderate.

### 5.3.1 Ides and Proteinuria

A phase I, first in man, double blind and randomized study with single ascending doses of IdeS has been conducted and the objective was to assess the safety, efficacy, pharmacokinetics, and immunogenicity of IdeS in healthy human subjects following intravenous administration.

A total of 29 healthy subjects were included and randomized into four dose groups. The subjects in each dose group were randomized to either IdeS or placebo. The starting dose was 0.01 mg/kg body weight (BW) ( $n_{\text{IdeS}} = 8$  and  $n_{\text{Placebo}} = 4$ ) and after evaluation by the data monitoring committee the dose was stepwise increased to 0.04 mg/kg BW ( $n_{\text{IdeS}} = 4$  and  $n_{\text{Placebo}} = 2$ ), 0.12 mg/kg BW ( $n_{\text{IdeS}} = 4$  and  $n_{\text{Placebo}} = 1$ ) and 0.24 mg/kg BW ( $n_{\text{IdeS}} = 4$  and  $n_{\text{Placebo}} = 2$ ). The subjects were followed until day 64 after dosing with more intensive monitoring during the first week. All subjects were male Caucasians with a median age of 23 years (range: 20-41), weight 76 kg (range: 59-100) with a body mass index of 23 kg/m^2 (range: 20-30) and there were no statistical significant differences in demographics between the groups.

As part of the safety assessment urinalysis (U-glucose, U-hemoglobin and U-protein) was performed using Multistix (Siemens, Germany). The proteinuria was scored as negative, trace, +1 (0.3 g/L), +2 (1.0 g/L), +3 (3.0 g/L) and +4 ( $\geq 20$  g/L) according to the manufacturer's instructions. A transient and mild proteinuria was observed 24-48 hours after dosing in subjects administered an IdeS dose that resulted in significant cleavage of IgG (Fig. 16). In the placebo treated group the proteinuria varied between negative and +1 during the 64 day period. In the highest dose group, where IgG was fully cleaved into  $F(ab')_2$  and Fc within 2-6 hours, peak levels of proteinuria at +2 was observed in three of four subjects. This peak probably reflected the clearance of IgG cleavage products from the circulation. None of the treated subjects had a strong elevation in proteinuria and in all subjects the values were rapidly normalized. No subjects had any signs of hematuria correlating to IdeS treatment.

[figure not shown]

Figure 16. Proteinuria was monitored as a safety assessment throughout the study. Multistix (Siemens) were routinely used at the hospital and transient proteinuria was detected in several subjects which correlated to IgG cleavage. A) Subjects given placebo ( $n = 9$ ). B) Subjects given a single dose of 0.24 mg/kg BW IdeS ( $n = 4$ ). Data represents proteinuria in individual subjects at the indicated time-points after treatment.

To minimize adverse outcomes, patients with extended criteria donors (ECD) will be excluded from the study. The level of proteinuria post IdeS is not clinically significant since proteinuria rapidly decreases to baseline day 3-4 after IdeS® administration. Proteinuric effects of IdeS will be monitored closely post IdeS for the first 4 weeks after transplant (see appendix A) to determine if there is a sustained effect.

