### 3 Primary Objectives

This study will be an open label design to assess the efficacy of IdeS® in eliminating DSAs in HS patients who are DSA+ and flow cytometry (FCMX) crossmatch + at time of transplant. Safety determinations will be aimed at assessments of any side effects associated with IdeS® administration and risk for infectious complications associated with IdeS® therapy for prevention of ABMR. Limited efficacy determinations will include incidence of allograft rejection, DSA levels at multiple times post-transplant (Day 0, 30, 90 and 180), determinations of renal function, proteinuria (day 0 through day 30), and pathologic assessments of allograft biopsies at 6M after completion of IdeS® therapy. Patients will be followed and assessed for infectious risk after transplantation as well.

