## Appendix A

**Study/Protocol Title: "A Phase I/II Trial to Evaluate the Safety & Tolerability of the Human IgG endopeptidase (IdeS®) for Elimination of DSAs & Prevention of Antibody-Mediated Rejection Post-Transplant in Highly-HLA Sensitized Patients"**

Study visit	Screening	Transplant Day 0	1 h ± 15 min	2h ± 15 min	6h ± 30min	Day 1 ± 2h	Day 2 ± 2h	Day 3 ± 6h	Day 4 ± 1d	Day 5 ± 1d	Day 7 ± 3d	Day 14 ± 3d	Day 21 ± 3d	Day 30 ± 3d	Day 90 ± 7d	Day 180 ± 30d
Prophylaxis: Ganciclovir for inpatients and Valganciclovir for outpatients	X															
Serum IgG		X													X	X
PPD/Quantiferon Test	X															
Informed Consent	X															
Inclusion/Exclusion criteria review	X															
Medical History	X															
Complete Physical Exam	X	X				X	X	X	X	X	X	X	X	X	X	X
Vital signs/weight	X	X				X	X	X	X	X	X	X	X	X	X	X
12-lead ECG (SOC)- w/in 6M	X															
Chest X-Ray (SOC) --w/in 6M	X															
Safety laboratory tests (CBC, CMP, UA)	X	X				X	X	X	X	X	X	X	X	X	X	X
Urine Total Protein, Urine Creatinine (UTP/UCr) (if urine available)		X				X	X	X	X	X	X	X				
Review Historical Serologies for HIV, HBV, HCV, CMV, & EBV	X															

EBV, CMV, PBK, PJC DNA PCR	X												X	X	X		
Pregnancy test (for WOCP)	X	X															
Estimated GFR (using MDRD equation)	X	X				X	X	X	X	X	X	X	X	X	X		

Study visit	Screening	Transplant Day 0	1 h ± 15 min	2h ± 15 min	6h ± 1h	Day 1 ± 6h	Day 2 ± 6h	Day 3 ± 6h	Day 4 ± 6h	Day 5 ± 1d	Day 7 ± 2d	Day 14 ± 3d	Day 21 ± 7d	Day 30 ± 7d	Day 90 ± 14d	Day 180 ± 30d
Pneumococcal Vaccine & Meningococcal Vaccine (Menactra® & Menomune®)	X															
Desensitization w IVIG + Rituximab*	X															
Screen ADA (Freeze and batch out/analyze at the end of the study)	X															
ADA (Sent Out)		X (pre-dose)				X					X	X		X	X	X
C3, C4 Levels								X						X		
PD analysis (Sent Out)		X (pre-dose)	X		X	X					X		X	X	X	
PK analysis (Sent Out)		X (pre-dose)	X	X	X	X	X	X	X	X	X	X				
Donor Specific Antibodies (DSA)		X			X	X								X	X	X
IdeS® Administration		X														
Alemtuzumab Administration**									X							
Ciprofloxacin Prophylaxis daily x 30d		X					X	X	X	X	X	X	X	X	X	
Repeat IVIG Post Tx											X					

CNI Levels							X	X	X	X	X	X	X	X	X	X	X	X
Allograft biopsy																		X
Adverse Event Monitoring			X				X	X	X	X	X	X	X	X	X	X	X	X

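### Quantitative urine protein (UTP/UCr) stops at Day 14 in Appendix A, so the last two weeks of the stated proteinuria window rest on urinalysis alone

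*Combined protocol and SAP*

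**What the plan says.** Three places in the combined protocol and SAP bear on this point.

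- **Section 3 (Primary Objectives)** lists, among the limited efficacy determinations, "determinations of renal function, proteinuria (day 0 through day 30"). No assay is named.
- **Section 5.3.1 (Ides and Proteinuria)** states "Proteinuric effects of IdeS will be monitored closely post IdeS for the first 4 weeks after transplant (see appendix A"), and gives the purpose as "to determine if there is a sustained effect". Again no assay is named. The same paragraph expects that "proteinuria rapidly decreases to baseline day 3-4 after IdeS® administration".
- **Appendix A** has one row devoted to urine protein, "Urine Total Protein, Urine Creatinine (UTP/UCr) (if urine available"), marked at Day 0, 1, 2, 3, 4, 5, 7 and 14. A separate row, "Safety laboratory tests (CBC, CMP, UA"), is marked at screening and at every day-level visit from Day 0 to Day 180. The components of the urinalysis are not listed.

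The proteinuria data behind Section 5.3.1 come from the phase I study in healthy men, where "urinalysis (U-glucose, U-hemoglobin and U-protein) was performed using Multistix (Siemens, Germany").

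**The concern.** Section 5.3.1 sets a question (does proteinuria persist?), gives it a four-week window, and sends the reader to Appendix A for the schedule. The quantitative row there ends about halfway through that window. A site that follows Appendix A will collect no UTP/UCr at Day 21 or Day 30.

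The question matters because the expectation of a brief, mild effect rests on healthy volunteers with a median age of 23. Only four of them received 0.24 mg/kg, the dose planned here. In this trial the drug is given around the implantation of a new graft, and Section 7 makes safety the primary aim. If the late values exist only as urinalysis, the second half of the window is measured on a coarser scale than the first, and the two cannot be read as one series.

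**Working it through.** No sample-size or power calculation applies. The check sets the stated window against the scheduled collections.

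**1. The stated window.** Section 3: Day 0 to Day 30. Section 5.3.1: 4 weeks = 4 × 7 = Day 28.

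**2. The schedule.** The header of Appendix A has 16 visit columns, from screening to Day 180. As extracted, the UTP/UCr row and the safety-laboratory row each have 16 cells, so neither shows a column shift. Over the stated window they read:

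| Row | D0 | D1 | D2 | D3 | D4 | D5 | D7 | D14 | D21 | D30 |
|---|---|---|---|---|---|---|---|---|---|---|
| UTP/UCr | X | X | X | X | X | X | X | X | – | – |
| Urinalysis (within safety labs) | X | X | X | X | X | X | X | X | X | X |

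The urinalysis row reproduces the Day 0 to Day 30 window. The UTP/UCr row does not.

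**3. Size of the gap.**
- Post-dose day visits to Day 30: Day 1, 2, 3, 4, 5, 7, 14, 21 and 30, nine in all. UTP/UCr is marked at seven of them.
- From the last UTP/UCr to the end of the window: 28 − 14 = 14 days, or 30 − 14 = 16 days.
- The header over this row allows Day 14 ± 3 days, so the latest scheduled value falls on Day 17. The gap is then 28 − 17 = 11 days, or 30 − 17 = 13 days.

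**4. What the existing UTP/UCr schedule can test.** Section 5.3.1 expects a return to baseline at Day 3–4. UTP/UCr is marked at Day 4, 5, 7 and 14, so it runs 14 − 4 = 10 days beyond the expected resolution. Persistence to Day 14 is measured quantitatively.

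**5. What urinalysis adds at Day 21 and Day 30.** This step assumes that the urinalysis includes a dipstick protein reading like the one in phase I. Those scores were anchored at 0.3, 1.0 and 3.0 g/L for +1, +2 and +3. The steps are 1.0/0.3 = 3.3-fold and 3.0/1.0 = 3-fold. Placebo subjects ranged from negative to +1 over 64 days, and three of the four subjects at 0.24 mg/kg peaked at +2. The peak effect was thus one category above the placebo range. A sustained effect at the +2 level could be seen on such a scale; one at +1 would lie within the range seen on placebo. The dipstick gives a concentration and UTP/UCr is indexed to creatinine, so the two do not form one series.

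**6. Effect of the change.** Adding Day 21 and Day 30 takes UTP/UCr from 8 to 10 scheduled collections and moves the last one from Day 14 to Day 30. The added tests number at most 2 × 20 patients = 40.

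**The case against.** The strongest case on the other side is that nothing promised is left unmeasured. Neither Section 3 nor Section 5.3.1 names UTP/UCr. Urinalysis is scheduled at Day 21 and Day 30, and again at Day 90 and Day 180. It is also the method that produced the phase I proteinuria data. UTP/UCr already continues well past the expected return to baseline. On this view the plan uses a dense quantitative schedule early and a simpler check later.

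Most of this stands, and it limits the point. A reader might infer that the sections depend on UTP/UCr specifically, that the question of a sustained effect cannot be answered as scheduled, or that a late rise could be neither shown nor excluded. The documents do not support these readings: the text leaves the assay open, persistence to Day 14 is quantified, and a late effect of the size seen at the phase I peak could show on urinalysis.

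Two cautions also stand. First, other rows of Appendix A look damaged in the extracted text; the row for calcineurin-inhibitor levels, for example, carries 12 marks for 11 post-transplant day visits. Equal cell counts rule out a column shift in the two rows used here but cannot prove that no mark was lost. Second, a change-from-Day-0 analysis would be fragile. Patients have end-stage renal disease and urine is collected only when it can be obtained, so a Day 0 value may be missing or may reflect the native kidneys.

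What the objection does not remove is the mismatch. Section 5.3.1 points to Appendix A for close four-week monitoring, and the dedicated row stops at Day 14 with no statement that urinalysis is meant to serve the remainder.

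**Conclusion.** The point holds as an inconsistency between text and schedule with a modest consequence. Persistence of proteinuria can be assessed quantitatively only to Day 14; at Day 21 and Day 30 it rests on urinalysis alone. The shortfall is two of nine post-dose day visits, or 16 days to Day 30 (13 at the late edge of the Day 14 window).

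This rests on two assumptions: that the UTP/UCr row as extracted matches the source table, and that the urinalysis yields a protein reading, which the protocol does not state. If it does not, no protein measurement is scheduled at those two visits.

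The added values would not settle causation. The trial is open label and every patient receives IdeS, so late UTP/UCr would describe proteinuria after transplant without by itself attributing it to the drug.

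**What to change.** In Appendix A, add UTP/UCr marks at Day 21 and Day 30, under the existing condition that urine can be obtained, so that the schedule matches Sections 3 and 5.3.1. In Section 7, state that UTP/UCr will be summarised by visit through Day 30, with the number of patients contributing at each visit. Persistence should be judged from the post-transplant values, not from change since Day 0.

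If the row is deliberately not extended, Section 5.3.1 should at least say which measure serves the Day 30 assessment, and Appendix A should list the urinalysis components.

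The cost is two marks in the table and up to 40 spot urine tests, fewer where no urine is available, at visits that already collect urine. No new visit is needed.
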